#### **5.3.4. Phase 2 Safety Population**

The Phase 2 safety population includes all subjects enrolled in the Phase 2 portion of the study who received at least 1 dose of INCB024360 or MEDI4736. Treatment groups for this population will be determined according to the tumor type at the time of enrollment on Day 1. All Phase 2 safety analyses will be conducted using the Phase 2 safety population.

#### **5.3.5. Pharmacokinetic [REDACTED] Evaluable Population**

The PK [REDACTED] evaluable population will include all subjects who received at least 1 dose of INCB024360 and provided at least 1 postdose plasma sample (1 PK [REDACTED] measurement). The study pharmacokineticist will review data listings of subject dose administration and sample records to identify subjects to be excluded from analyses of PK data. [REDACTED]

[REDACTED]

## 6. BASELINE, EXPOSURE, AND DISPOSITION VARIABLES AND ANALYSES

Sample data displays are provided in [Appendix C](#). Data from Phase 1 and 2 portions will be summarized separately where appropriate.

### 6.1. Baseline and Demographics, Physical Characteristics, and Disease History

The following demographic and baseline characteristics will be summarized for the ITT population: age, sex, race, ethnicity, weight, height, ECOG performance status, staging, prior radiation (yes/no), prior surgery (yes/no), prior systemic therapy other than radiation (yes/no), date of diagnosis, and primary tumor histology.

### 6.2. Disposition of Subjects

The number and percentage of subjects who were enrolled and who were withdrawn from the study (with a primary reason for withdrawal) will be summarized for the ITT and safety populations.

### 6.3. Protocol Deviations

Protocol deviations captured on the Protocol Deviation Log will be presented in the subject data listings.

### 6.4. Exposure

For subjects in the ITT and safety populations, descriptive statistics will be provided by cohort; number of cycles; duration of treatment; average daily dose (mg) and total dose (mg) of INCB024360; and number of doses, relative dose intensity (mg/kg), and average dose (mg/kg) of MEDI4736.

- **Number of Cycles:** Number of cycles for INCB024360 will be the number of cycles with a nonzero dose of INCB024360.
- **Duration of Treatment:** The number of study days between Day 1 and the last nonzero dose administration record of INCB024360 or MEDI4736 taken by the subject.
- **Number of Doses of MEDI4736:** Number of doses of MEDI4736 for a subject will be the number of administered, scheduled infusions of MEDI4736 recorded on the MEDI4736 Dosing CRF.
- **Average Doses of MEDI4736 (mg/kg):** The average dose of MEDI4736 (in mg/kg) will be the sum of the doses of MEDI4736 recorded on the MEDI4736 Dosing CRF divided by the number of doses of MEDI4736.

Treatment with MEDI4736 will be discontinued after 12 months of treatment. Discontinuation of MEDI4736 treatment may also be considered for subjects who have attained a confirmed complete response (CR). Subjects may continue on INCB024360 monotherapy at this time.

Subjects who then report radiographic disease progression will be eligible for re-treatment with MEDI4736 at the discretion of the investigator if no cancer treatment was administered other than INCB024360 and the subject meets the safety parameters listed in the inclusion/exclusion criteria. Subjects will resume therapy at the same dose and schedule at the time of initial discontinuation. Number of doses, average doses, and dose intensity for MEDI4736 in this re-treatment phase will be summarized separately and then combined with all previous doses.

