4. INVESTIGATIONAL PLAN

4.1. Overall Study Design

This is a Phase 1/2 open-label study of epacadostat administered in combination with durvalumab in subjects with advanced melanoma, NSCLC, pancreatic cancer (Phase 1 only), SCCHN, TNBC, gastric or GE junction cancer, or TCC of the GU tract. The dose-escalation part of the study (Phase 1) uses a 3 + 3 design to identify the MTD or PAD of epacadostat in combination with durvalumab. Phase 2 will further explore the safety and efficacy of the MTD or PAD of epacadostat in combination with durvalumab determined in Phase 1.

The study will consist of 3 periods:

Screening: Up to 28 days.

Treatment Period: The treatment period will continue every 14 days for up to 12 months as long as subjects are receiving benefit from treatment and have not met any criteria for study withdrawal as defined in Section 5.7.1. Once subjects complete 12 months of study treatment or permanently discontinue study treatment for any other reason, the EOT visit should be conducted, and they should enter the follow-up period of the study.

Follow-Up Period: The safety follow-up visits will occur at 42 days (± 7 days) and 90 days (± 7 days) after the EOT visit or the last dose of study treatment if the EOT visit is not completed.

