5.7. Withdrawal of Subjects From Study Treatment

5.7.1. Withdrawal Criteria

Subjects **must** be withdrawn from study treatment for the following reasons:

- The subject completes 12 months of study treatment with epacadostat and durvalumab, or had completed 12 months of combination treatment (prior to Amendment 6 [28 JUN 2017]), and has taken epacadostat monotherapy for an additional 12 months (for a total of 24 months of study treatment).
 - Note: A subject may be granted an exception by the medical monitor to continue on epacadostat monotherapy beyond 24 months of overall treatment duration if they are clinically stable or clinically improved. Approvals to remain on epacadostat monotherapy will require continuing review every 3 months.
- In the investigator's medical judgment, further participation would be injurious to the subject's health or well-being.
- The subject becomes pregnant.
- Consent is withdrawn by subject or legal representative (such as legal guardian).
- The subject has experienced an unacceptable toxicity as described in Section 5.6 or a toxicity that does not recover in 4 weeks. Investigators who wish to continue treatment after a treatment delay of 4 weeks should consult with the sponsor's medical monitor for approval.
- Confirmed radiographic progression of disease per modified RECIST v1.1. See Section 7.4 for details on subjects with unconfirmed radiographic progression. An exception to continue on treatment with confirmed radiographic progression may be granted to clinically stable subjects. See Section 7.4 for additional details.
- The study is terminated by the sponsor.
- The study is terminated by the local health authority or IRB or IEC.
- \geq Grade 3 infusion reaction.
- Initiation of alternative anticancer therapy including another investigational agent.

A subject **may** be withdrawn from the study treatment as follows:

- If subject attains a CR (see Section 7.4.3), and the decision is made to discontinue durvalumab.
- If, during the course of the study, a subject is found not to have met eligibility criteria, the medical monitor, in collaboration with the investigator, will determine whether the subject should be withdrawn from study treatment. See Section 11.3, Protocol Adherence.
- If a subject is noncompliant with study procedures or study drug administration in the opinion of the investigator, the sponsor should be consulted for instruction on handling the subject.

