APPENDIX E. PROTOCOL AMENDMENT SUMMARY OF CHANGES

Document	Date
Amendment (Version) 1:	29 SEP 2014
Amendment (Version) 2:	20 FEB 2015
Amendment (Version) 3:	10 JUL 2015
Amendment (Version) 4:	12 JAN 2016
Amendment (Version) 5:	25 MAY 2016
Amendment (Version) 6:	28 JUN 2017
Amendment (Version) 7:	21 SEP 2018

Amendment 7 (21 SEP 2018)

Overall Rationale for the Amendment:

The primary purpose of this amendment is to reduce required study procedures and update guidelines on the management of legacy subjects who remained on epacadostat monotherapy.

This amendment includes the changes to INCB 24360-203 Protocol Amendment 6 (28 JUN 2017) summarized below.

1. **Synopsis; Section 5.4, Duration of Treatment and Subject Participation; Section 5.7.1, Withdrawal Criteria; Section 6.2, Treatment Period; Section 6.2.1, Restarting Treatment With Study Therapy After Treatment Withdrawal; Section 7.3.6, Laboratory Assessments; Section 7.3.7, Chest Radiograph; Section 7.4.2, Tumor Imaging During the Study; Appendix F, Re-Treatment**

Description of change: The duration of epacadostat monotherapy treatment for any subject taking epacadostat monotherapy at the time of Amendment 6 and allowed to remain on the monotherapy regimen was capped at 12 months, thereby also capping overall treatment duration maximum for these subjects at 24 months. Exceptions will require medical monitor review and approval every 3 months. The option for subjects who completed 12 months of combination therapy with SD or better, to restart study therapy post-progression was removed.

Rationale for change: The sponsor has decided to cap the duration of epacadostat monotherapy and remove the option to restart combination therapy post-progression based on emerging data, from the Phase 3 KEYNOTE-252/ECHO-301 study in advanced or metastatic melanoma.

2. **Section 1.2, Study Rationale**

Description of change: Language regarding the results of the ECHO-301/KEYNOTE-252 study eDMC review was added.

Rationale for change: To provide updated data regarding the rationale of epacadostat and anti-PD-(L)-1 combination therapy.

3. **Section 1.3.1, Risks from Epacadostat; Section 5.6.4, Procedures for Subjects Exhibiting Serotonin Syndrome; Section 5.10.2, Prohibited Medications and Measures; Appendix C, Publication on Serotonin Syndrome**

Description of changes: Protocol text relevant to serotonin syndrome was updated. Prohibition of concomitant melatonin supplements was lifted. Appendix C was removed.

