2. Synopsis; Section 4.1, Overall Study Design; Section 5.1.1, Epacadostat; Section 5.4, Duration of Treatment and Subject Participation; Section 5.6.2, Criteria and Procedures for Interruption or Dose Reduction; Section 5.7, Withdrawal of Subjects from Study Treatment; Section 6, Study Assessments (Table 21: Schedule of Assessments); Section 6.2, Treatment Period; Section 6.2.1, Restarting Treatment With Study Therapy After Treatment Withdrawal; Section 6.4.2, Follow-Up; Section 7.3.6, Laboratory Assessments; Section 7.3.7, Chest Radiograph; Section 7.4.2, Tumor Imaging During the Study; Appendix F: Re-Treatment

Description of change: The epacadostat monotherapy treatment option was removed from the Protocol. Relevant sections were modified to allow for restarting combination therapy upon evidence of disease progression under certain conditions and to allow for subjects to be re-treated with durvalumab monotherapy upon evidence of disease progression if the combination therapy was not tolerated in the initial treatment period

due to a toxicity attributed to epacadostat, but they completed 12 months of durvalumab and had a status of stable disease or better when they discontinued treatment.

Rationale for change: Based on emerging data with regard to epacadostat monotherapy as well as monotherapy data from other agents targeting the IDO pathway, there is no clear evidence of antitumor activity with IDO inhibitors as monotherapy in the tumors being evaluated in this study. IDO1 is an interferon response gene and a resistance mechanism to PD-1 pathway targeting agents. Based on Phase 2 studies, augmenting activity of PD-1 pathway–targeting agents has been reported in tumor types where PD-1 pathway–targeting agents have been approved by regulatory authorities. Thus, responders who complete 12 months of treatment and discontinue study treatment may resume combination therapy.

3. Synopsis; Section 3.3, Subject Exclusion Criteria

Description of changes:

- a. Exclusion criteria 1e and 1f were revised to remove alkaline phosphatase and update requirements for aspartate aminotransferase, alanine aminotransferase, and total bilirubin.
- b. Criterion 7 was revised to exclude subjects with major surgical procedure within 28 days of starting study treatment OR inadequate recovery from toxicity and/or complications from major surgery before starting study treatment.
- c. Criterion 9 was revised to include carcinomatous meningitis and define CNS metastases.

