## **2. STUDY INFORMATION, OBJECTIVES, AND ENDPOINTS**

### **2.1. Protocol and Case Report Form Version**

This SAP is based on INCB 24360-203 Protocol Amendment 1 dated 29 SEP 2014 and case report form (CRF) approved on 08 SEP 2014. Unless superseded by an amendment, this SAP will be effective for all subsequent Protocol amendments and CRF versions.

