**Table 7: RECIST Evaluation Criteria for Objective Response: Measurable Disease at Baseline**

Target Lesions	Nontarget Lesions	New Lesions	Overall Response
CR	CR (or no nontarget lesion)	No	CR
CR	Non-CR/non-PD	No	PR
CR	NE	No	PR
PR	Non-PD and NE (or no nontarget lesion)	No	PR
SD	Non-PD and NE (or no nontarget lesion)	No	SD
Not all evaluated	Non-PD	No	NE
PD	Any	Yes or No	PD
Any	PD	Yes or No	PD
Any	Any	Yes	PD

PR = partial response.

A subject is considered an objective responder as assessed by mRECIST if they have an overall response of CR or PR at any postbaseline visit. The proportion of responders within each treatment group will be estimated with 95% CIs by treatment group. Confidence intervals will be calculated based on the exact method for binomial distributions.

In general, best response is determined on subject level using the highest overall response achieved postbaseline. In the case of SD, measurements must meet the SD criteria at least once after study entry at a minimum interval of 56 ( $\pm 7$ ) days. Subjects who fail to meet these criteria will have best response of PD if the next available RECIST evaluation after the initial scan indicates PD or NE if there are no additional RECIST evaluations available.

A sensitivity analysis for the primary endpoint will be performed in response evaluable population.

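### SAP 6.4 provides for re-treatment after progression, which the current Protocol does not, and the response and treatment-duration rules have no stop at a second course

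*SAP*

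**What the plan says.** **Re-treatment.** SAP 6.4 has durvalumab stop after 12 months, or possibly after a confirmed CR, with epacadostat alone optional from then on. It continues: "Subjects who then report radiographic disease progression will be eligible for re-treatment with MEDI4736 at the discretion of the investigator". The SAP rests on Protocol Amendment 1, and its Table 15 lists only the original of 26 NOV 2014. SAP 2.1 nevertheless keeps it in force: "Unless superseded by an amendment, this SAP will be effective for all subsequent Protocol amendments and CRF versions".

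The current Protocol (Amendment 7) has no such path. Section 4.1 says: "Once subjects complete 12 months of study treatment or permanently discontinue study treatment for any other reason, the EOT visit should be conducted", with follow-up next, and Section 6.2 says the same. Section 5.7.1 lists among the mandatory reasons for withdrawal from study treatment: "The subject completes 12 months of study treatment with epacadostat and durvalumab". The only continuation it describes is for legacy subjects already on epacadostat monotherapy.

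**Response.** SAP 7.3.1 and Protocol 9.4.1 both count a subject as a responder on a CR or PR at any visit after baseline. SAP 7.3.1 adds: "best response is determined on subject level using the highest overall response achieved postbaseline". SAP 4.1.4 fixes baseline before the first dose of either drug. No rule closes the response window when a second course starts.

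**Exposure.** SAP 6.4 defines Duration of Treatment as: "The number of study days between Day 1 and the last nonzero dose administration record of INCB024360 or MEDI4736 taken by the subject". For re-treatment it separates only the number of durvalumab doses, the average dose and the dose intensity, and then pools these with the earlier doses.

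**The concern.** The Phase 2 primary endpoint is ORR, set against low reference rates in Protocol Tables 33 and 34. A response that first appears on a second course, after progression on the first, is a different outcome from a response to the initial course. As the rules stand, the two go into the same numerator.

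Any shift is upward only. It can arise only in subjects enrolled early enough to finish a first course, progress and restart before Amendment 7. Such a subject would also have inconsistent endpoints: PFS (SAP 7.4.3) would end at the first progression, while DoR (SAP 7.4.2) would begin after that event.

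Duration of Treatment would be overstated for subjects who had an interval off both drugs. The SAP recognised that re-treatment needs separate handling, but applied this only to durvalumab dose summaries.

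**Working it through.** **1. Could second-course data exist?** The amendment log describes superseded text, so it is used here only as evidence of what was once allowed. For Amendment 6 (28 JUN 2017): "Relevant sections were modified to allow for restarting combination therapy upon evidence of disease progression under certain conditions". The same entry also allowed durvalumab alone in some cases. For Amendment 7 (21 SEP 2018), the option "to restart study therapy post-progression was removed"; that entry describes the option as open to subjects who had completed 12 months of combination therapy with SD or better. Subjects with a best response of SD were therefore among those eligible, and they are non-responders on the first course.

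**2. How wide was the window?** The Protocol synopsis estimates first enrollment at 29 OCT 2014, so early enrollees had years. A subject enrolled on 28 JUN 2017 would finish 12 months no earlier than 28 JUN 2018, leaving 85 days to 21 SEP 2018.

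**3. Reproduce the planned sizes.** Protocol 9.2.2 and Table 34 give H0 10%, Ha 30%, one-sided alpha 10%, power 90% and 10% loss. The smallest exact single-stage design is n = 25 with at least 5 responses (alpha 0.0980, power 0.9095). Then 25/0.9 = 27.8, rounded up to 28, which matches. The Table 33 Simon designs also meet their stated error rates (alpha / power): melanoma 0.0492 / 0.9009, TNBC 0.0500 / 0.9069, gastric and GE junction 0.0349 / 0.9018. The planned sizes are not in question.

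**4. Effect of one reclassified subject on ORR (1/n).**
- Expansion cohort, n = 28: 1/28 = 3.6 points. For example, 4/28 = 14.3% (exact 95% CI 4.0 to 32.7) becomes 5/28 = 17.9% (6.1 to 36.9).
- Melanoma, n = 40: 1/40 = 2.5 points.
- TNBC, n = 29: 1/29 = 3.4 points.
- Gastric and GE junction, n = 20: 1/20 = 5.0 points.

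**5. Range under assumed frequencies (not in the documents).** Let q be the share of a cohort that are re-treated first-course non-responders, and s their second-course response rate. The apparent rate is then p0 + q × s. With q from 5% to 15% and s from 10% to 30%, q × s runs from 0.005 to 0.045. In a cohort of 28 that is 28 × 0.005 = 0.14 to 28 × 0.045 = 1.26 extra responders on average. The false-positive rate of the rule of at least 5 in 25 would move from 0.098 to between 0.115 and 0.292. The upper end needs both assumptions at their maximum.

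**6. Duration.** With assumed lengths of 12 months on, 6 months off both drugs and 3 months on, the SAP definition gives 12 + 6 + 3 = 21 months, against 12 + 3 = 15 on treatment. For a 365-day first course, a second course of 90 to 365 days and a gap of 30 to 365 days (all assumed), the gap is between 30/760 = 4% and 365/820 = 45% of the reported duration.

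**The case against.** The case for a small effect is strong, and most of it stands.

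- **Few subjects can be affected.** Subjects re-treated after a CR are already responders. The others must complete 12 months without reaching PR, progress, restart, and then shrink at least 30% below the original baseline sum. Any new lesion makes the assessment PD (SAP Table 7).
- **Simon decisions.** A reader might infer that one second-course responder could carry a cohort over its cut-off, for example from 16 to 17 of 40. The documents do not support that as stated. SAP 3.3.2 suggests the first scheduled Week 8 assessment for both the stage 1 and the final count, which re-treatment after 12 months cannot reach. It is only a suggestion, and Protocol 9.2.2 does not repeat it. If it is used, the cut-offs are safe, but the reported ORR is still open.
- **No formal test.** Protocol 9.3 and SAP 3.2 state that no efficacy hypothesis is tested. The false-positive rates above illustrate sensitivity; they are not error rates of a planned test.
- **Off-drug time.** A reader might take the whole interval between courses as time off drug. SAP 6.4 lets subjects stay on epacadostat, and those subjects were off durvalumab only. The table shells also show days of exposure for each drug, though the SAP does not define how these are derived.
- **Cut-off at PD.** Closing the response window at confirmed PD would go too far. Protocol 7.4.3.3.4 allows treatment beyond confirmed PD, and a response during that continued first course is not a re-treatment response.
- **Separate schedule.** Re-treatment had its own appendix, since removed. Whether its scans were stored with the primary response data cannot be determined from these documents.

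None of this supplies the missing rule. The any-visit definition is also in the Protocol, so both documents need the change.

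**Conclusion.** The point holds as a gap in the analysis rules and should be fixed. SAP 6.4 conflicts with Protocol 4.1, 5.7.1 and 6.2. Which re-treatment rule applies is for the sponsor to settle, and nothing here favours either. Whatever the answer, the responder, best-response and duration rules as written would take in a second course.

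The documents do not show that the ORR has been inflated. They give no count of re-treated subjects, and the number who could change from non-responder to responder is probably small. The firm figures are the per-subject ones: 3.6 points at n = 28, 2.5 at n = 40, 3.4 at n = 29 and 5.0 at n = 20. The ranges in steps 5 and 6 of the working rest on assumed frequencies and lengths. PFS is unaffected because it ends at progression, and the planned sample sizes stand.

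**What to change.** 1. Reconcile SAP 6.4 with Protocol 4.1, 5.7.1 and 6.2, and state in the SAP how data from any legacy re-treatment are handled.
2. In SAP 7.3.1 and 7.4.2 and in Protocol 9.4.1, derive ORR, best response and DoR from assessments made before the start of any re-treatment course or new anticancer therapy. Do not truncate at confirmed PD for subjects continuing their initial course.
3. In SAP 6.4, compute duration of treatment by course and leave out intervals off both drugs. Time on epacadostat alone remains treatment time.
4. List re-treatment responses and exposure separately, with the number of re-treated subjects in each cohort.

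The cost is wording in both documents and a small programming change: one cut-off date per subject in the response derivation and a by-course sum for exposure. No new data are needed beyond course start and stop dates and the start of new therapy. The reported ORR may be slightly lower.

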## **6.5. Study Drug Compliance**

For subjects in the ITT and safety populations, overall compliance (%) for INCB024360 will be calculated for all subjects as follows:

$$\text{Overall Compliance (\%)} = 100 \times [\text{total dose taken}] / [\text{intended dose}]$$

The intended dose will be determined up to the earliest study day of permanent discontinuation of INCB024360 (ie, AE discontinuation is the first AE with action taken being "drug withdrawn"), last study drug record in the database, or subject death. Intended dose is defined as the sum of the doses prescribed by the investigator accounting both for planned dose reductions as well as those reductions or increases mandated by the investigator.

